#### Data Analysis Plan:

### STATISTICAL METHODS & POWER CALCULATIONS

**Overview.** In all analyses for Aim 1 and Aim 2, primary inference will be drawn based on intention to treat (ITT) analyses. Average complier effect (ACE) will be used to inform the metformin effect under full compliance to treatment assignments (Angrist et al, 1996). Per protocol analyses will be used to inform the metformin effect among completers. All analyses will be carried out unadjusted and with adjustment for covariates (Table 7) and covariate interactions with treatment and time. Corrections for multiple comparisons will be applied as appropriate.

The impact of metformin treatment on the progression of frailty status (non-frail, pre-frail, frail) over time will be assessed with a repeated measures mixed effects multinomial logistic model that models the log-odds of adjacent frailty statuses in terms of an indicator of metformin use, time, and the metformin use by time interaction. The possibility of non-linear trends of the log-odds of frailty statuses will be assessed by including an additional time factor (e.g., time squared) and its interaction with metformin use. The best fitting model will be used for inference. Secondary outcomes including gait speed, 6 minute walk, SPPB, frailty index constructed from the research data collected according to the Rockwood index (Searle et al., 2008; Rockwood et al., 2007), and body composition will similarly assessed. Under the linear trend model, the beneficial impact of metformin will be revealed by a significant time by treatment interaction associated with the log-odds of frailty status progression, indicating that the rate of increase in the likelihood of frailty progression over time is reduced in the metformin arm relative to the placebo arm. Under the non-linear trend model, the impact of metformin will be revealed by a significant reduction in the log-odds of frailty status progression in the metformin arm versus placebo at certain time points during the follow-up. SAS proc **nlmixed** will be used in the mixed effects model analyses. Proc **nlmixed** is preferred over other mixed effects modeling procedures such as GEE because it is valid under missing at random (MAR) assumption, accommodates linear and non-linear modelling, and uses maximum likelihood estimation.

Table 7. Covariates included in statistical analyses

Categories of covariates	Baseline	Time Varying
Demographics (age, sex)	X	
BMI (obesity), sarcopenia	X	X

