**3.D.3. Power Calculation for Aim 1.** With 60 completers per arm, this study will achieve a power of 86% to detect an overall odds ratio of 0.20 for a one ordinal category increase in the frailty score in metformin versus placebo based on SAS **proc nlmixed** analyses of 1000 simulated databases with 6 repeated measures per subject, all subjects at frailty score 0 or 1 at baseline, an increasing random pattern in the placebo group, a pattern of lower frailty scores with increasing time on study in the treated group, and 10% of subjects in each arm remaining at baseline levels throughout all subsequent visits, two-sided testing, and a significance level of 5%.  At visits 1 through 6 Placebo subjects were assigned a 56% chance of increasing by one level, 22% staying the same, and 22% decreasing by one frailty level, and Treated subjects were assigned a 33% chance of increasing by one level, a 33% chance of staying the same, and a 33% chance of decreasing by one frailty level relative to the previous visit. With these parameter values, at baseline 50% of subjects were at frailty level 0 and 50% at level 1 in each arm and at visit 6 the distributions for Placebo were 0: 25%, 1: 22%, 2: 20%, 3: 18%, 4: 11%, 5: 4% on the average across the 1000 simulations. Distributions for Treated were 0: 50%, 1: 24%, 2: 14%, 3: 11%, 4: 0%, 5: 0% on the average across the 1000 simulations.

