**3.D.6. Time to major adverse event.** The relation between treatment and time to major adverse outcome will be studied with and without adjustment for covariates and will be described with Kaplan-Meier curves. An adverse outcome will be defined as a) 2 point increase in the frailty score, or b) fall resulting in bone fracture or other serious injury, c) admission to a nursing home or skilled care facility, or d) death. The time to adverse outcome will be defined as the time to first occurrence of any of a), b), c) or d) and will otherwise be considered censored at loss to follow-up or end of study. Without adjustment, treatment groups will be contrasted on time to major adverse outcome with a logrank test and the treatment-specific accumulated incidence of adverse outcome will be described with Kaplan-Meier curves and 95% confidence bands. An adjusted contrast of treatment groups will be carried out with a Cox proportional hazards model in terms of treatment group, age, ethnicity, gender, and baseline values of frailty score. OGTT and inflammatory biomarkers will be entered as time-dependent covariates. Logrank testing, Kaplan-Meier estimates of survival distributions, and covariate adjusted Cox modelling of relative risks accommodate non-informative right censored survival data.

**3.D.7. Missing Data.** Limited missingness in outcomes and associated covariates is possible due to loss to follow-up. Missing covariates without loss to follow-up may occur due to missed appointments and intercurrent illness. In the primary analyses, model estimates will be derived based on the likelihood of observed data, an approach that gives consistent estimates under the MAR assumption: “missingness” depending upon the observed data but not the unobserved. To further address the possibility of missing data under the MAR assumption, we will conduct all analyses without and with multiple imputation using SAS proc mianalyze and its companion procedure proc mi. The mianalyze procedure combines the results of the analyses of imputations and generates valid statistical inferences and MI creates multiply imputed data sets for incomplete multivariate data.

**3.D.8. Randomization.** Participants will be randomized to metformin or placebo in a balanced design.

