3.3.9. Blinding. This study is double blinded. Only the study pharmacist has knowledge of the medication each participant is taking. As per the requirement by the NIA-appointed DSMB, one study statistician has been and will remain unblinded. The unblinded study statistician will prepare DSMB reports as per the guidelines provided from the National Institute on Aging (<https://www.nia.nih.gov/research/dgcg/clinical-research-study-investigators-toolbox/data-and-safety-monitoring>). Any unblinded report will be reviewed during a closed DSMB session with only the unblinded statistician present and without any study investigators present.

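### Section 3.D.6 counts a 2-point frailty rise as a major adverse event and stops at the first event, so injurious falls, institutional admissions and deaths are never compared on their own

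*Combined protocol and SAP*

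**What the plan says.** Section 3.D.6 (Time to major adverse event) defines one composite: "An adverse outcome will be defined as a) 2 point increase in the frailty score, or b) fall resulting in bone fracture". Component b) also takes in falls that cause another serious injury; c) is entry to a nursing home or skilled-care facility, and d) is death. The event-time rule is "The time to adverse outcome will be defined as the time to first occurrence of any of a), b), c) or d"). The planned comparison is that "treatment groups will be contrasted on time to major adverse outcome with a logrank test", with Kaplan-Meier curves and an adjusted Cox model on the same composite. No component is tabulated or tested separately.

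Frailty is also the Aim 1 outcome. The Overview of the statistical methods says "The impact of metformin treatment on the progression of frailty status (non-frail, pre-frail, frail) over time will be assessed", and section 3.D.3 powers the trial on "an overall odds ratio of 0.20 for a one ordinal category increase in the frailty score".

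The other outcomes compared by arm are not clinical harms: "Secondary outcomes including gait speed, 6 minute walk, SPPB, frailty index constructed from the research data", body composition, and the insulin-sensitivity and inflammation markers of Aim 2. The Blinding paragraph adds that "The unblinded study statistician will prepare DSMB reports as per the guidelines provided from the National Institute on Aging". It does not say what those reports tabulate.

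**The concern.** Component a) is an efficacy measure. Components b) to d) are the serious clinical events a reader would look for under a heading about major adverse events. Pooling them has two effects.

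- If metformin reduces frailty as planned, a) supplies most events and favours metformin. The composite then largely repeats the Aim 1 result and can show a benefit while b) to d) are more frequent on metformin.
- Under the first-event rule, a participant who rises 2 points at month 12 and dies at month 20 appears only as a frailty event at month 12. If metformin works, more placebo participants will already have had their first event, so later harms are dropped unequally between arms. Splitting first events by type would not repair this.

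At stake is whether the trial's planned results can show how many participants in each arm had a serious fall, an institutional admission or died.

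**Working it through.** **Nothing to reproduce.** Section 3.D.6 gives no event rate, hazard ratio or power. The check asks how large a) is on the plan's own figures, and what the composite then shows if b) to d) are worse on metformin.

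**Inputs from section 3.D.3.** 60 completers per arm; every participant at score 0 or 1 at baseline. Scores 0 to 5 at visit 6 are 25/22/20/18/11/4% on placebo and 50/24/14/11/0/0% on metformin (sums to 99%, rounding).

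**Size of a) at visit 6.** Everyone starts at 0 or 1, so anyone at 3 or more has risen at least 2 points (lower bound), and nobody below 2 has (upper bound).

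- Placebo: 18+11+4 = 33% up to 20+33 = 53%, or 20 to 32 of 60.
- Metformin: 11% up to 14+11 = 25%, or 7 to 15 of 60.

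Over both arms this is (19.8+6.6)/120 = 22% to (31.8+15)/120 = 39%. That is compatible with the 47-58% the protocol expects to worsen in frailty status. These are shares at one visit. Scores can fall back, so the share ever reaching a 2-point rise may be higher.

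**Assumptions.** The documents give no b) to d) rates. I take 3%, 5% and 10% of placebo participants over two years, constant and independent hazards, and visit 6 as end of follow-up. With λ = -ln(1-p), and k the b) to d) hazard ratio on metformin:

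composite HR = (λ_a,met + k·λ_h,pbo) / (λ_a,pbo + λ_h,pbo)

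For a), λ is 0.400 vs 0.117 (lower bounds, HR 0.29) and 0.755 vs 0.288 (upper bounds, HR 0.38). For b) to d) at 3%, 5% and 10%, λ is 0.0305, 0.0513 and 0.1054.

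Example at 5%, k = 2, lower bounds: (0.117 + 0.103) / (0.400 + 0.051) = 0.49.

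| Placebo b) to d) | Composite HR, k = 2 | Chance of significant benefit, k = 2 | Composite HR, k = 3 | k giving composite HR 1 |
|---|---|---|---|---|
| 3% | 0.41-0.44 | 69-82% | 0.48 | 10-16 |
| 5% | 0.48-0.49 | 55-75% | 0.55-0.60 | 6.5-10 |
| 10% | 0.58-0.65 | 28-55% | 0.70-0.86 | 3.7-5.4 |

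The chances use Schoenfeld's formula, 60 per arm, two-sided 5%. The ranges pair lower bound with lower and upper with upper. Crossing them at k = 2 gives 0.23-0.38 (53% vs 11%) or 0.81-0.99 (33% vs 25%), still not above 1.

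**Smaller frailty effect (assumed 20% vs 14% with a 2-point rise).** λ_a is 0.223 vs 0.151. With k = 2 the composite HR is 0.83, 0.92 and 1.10 at 3%, 5% and 10%. With b) to d) in 5% of placebo and 15% of metformin participants (k = 0.1625/0.0513 = 3.2) it is (0.151+0.163)/(0.223+0.051) = 1.14, towards harm.

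**What separate reporting would show.** With k = 2, participants with a b) to d) event number 1.8 vs 3.5 (3%), 3.0 vs 5.9 (5%) and 6.0 vs 11.4 (10%). Power for a formal test is 12%, 18% and 30%; 80% power needs 66 events (Schoenfeld) or 71 (Freedman).

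**The case against.** Four points can be made for the plan.

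**The composite may be meant as efficacy.** The abstract and background list falls, institutionalization and death as consequences of frailty, and the body of 3.D.6 speaks of an adverse outcome rather than of safety. None of the metformin side effects in the risk section is a component. This is a fair reading and supports keeping the composite as a secondary efficacy outcome. It does not justify the heading, and it leaves the plan with no between-arm analysis of serious clinical events at all.

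**By-arm safety review exists.** A reader might infer that nobody compares harms by arm during the trial. The documents do not support that: there is a DSMB, an unblinded statistician and closed-session reports. Deaths and injuries may well be in them. They are not, however, a planned analysis of the trial's results.

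**Masking is not inevitable.** A reader might infer that the frailty component always decides the result, or that the composite could never show harm. Both need a large frailty benefit. Section 3.D.3 assumes an odds ratio of 0.20, while the protocol's own observational estimate (metformin vs sulfonylurea) is 0.66. With 20% vs 14% the composite is near null or adverse. Simulating the step probabilities in 3.D.3 gives about 56% vs 26% with a 2-point rise. I do not rely on that: simple truncation at 0 and 5 does not reproduce the stated visit-6 distributions, and the implied 69% worsening of frailty category on placebo exceeds the protocol's 47-58%.

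**Harm is hypothetical and events are few.** No document figure suggests that metformin raises these events; the one mortality figure (hazard ratio 0.69 vs sulfonylurea) points the other way. Independence of a) and b) to d) is also a simplification, since the protocol says frailty predicts death and dependence. The low power stands in full, and it limits the remedy to description.

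**Conclusion.** The concern holds as a gap in the written analysis plan. Injurious falls, institutional admissions and deaths are compared by arm only inside a composite that includes the efficacy scale, and any that follow a 2-point rise are lost. That follows from the text and needs no assumption.

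How far the composite could mislead is conditional. If the frailty effect planned in 3.D.3 is real, with placebo b) to d) rates of 3-10%, constant independent hazards and matched bounds, a doubled b) to d) hazard on metformin would still give a composite hazard ratio of about 0.41-0.65. If the frailty effect is much smaller, the composite would not turn such harm into an apparent clear benefit and could point towards harm. In both cases the components go unreported. The documents support neither the conclusion that harms are unmonitored nor an expectation that metformin causes them.

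**What to change.** In section 3.D.6:

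- Report b) to d) together, and each of b), c) and d), by arm, counted whether or not a 2-point frailty rise came first. Give counts, rates and confidence intervals, with death treated as a competing event for b) and c).
- Keep the a) to d) composite with its logrank, Kaplan-Meier and Cox analyses as a secondary efficacy outcome, under a heading that does not call it an adverse event.
- State that the b) to d) comparison is descriptive.

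The cost is a few sentences. The events are already needed for the composite, provided that recording of b) to d) continues after a 2-point rise. The downside is few events and wide intervals, with roughly 12-30% power at a hazard ratio of 2, so the table must not be presented as a powered safety test.

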**Item 7 Risks Section:**

Complete the following table to describe the risks of all **research procedures** listed in Step 2, Institutional Form (items 28-34). *Do not list risks of Routine care procedures here.*

N/A, Risks are described in the informed consent document – do not complete this table.

Research procedures	Risks
example: 
 
History and physical
 
Questionnaire
 
Laboratory tests
 
	List the reasonably expected risks under the following categories as appropriate:
Add or delete rows as needed	

